
NAME OF COMPANY: Traverse Therapeutics, Inc.	NAME OF FINISHED PRODUCT: sparsentan tablets

hypothesis of interest is whether eGFR slopes over the blinded treatment period (after adjusting for early hemodynamic effects) are different between the 2 treatment groups, ie:
 $H_0: (\beta_{\text{time}*\text{treatment}} + \beta_{\text{time } k*\text{treatment}}) = 0 \text{ versus } H_1: (\beta_{\text{time}*\text{treatment}} + \beta_{\text{time } k*\text{treatment}}) \neq 0$ 
This hypothesis will be tested using the mixed model by testing whether the time-by-treatment interaction parameters least-squares (LS) mean estimate is equal to zero. Sensitivity analyses are planned to assess the potential impact of major protocol deviations, premature treatment discontinuations, changes in immunosuppressive medications, and the choice of the change point.
 
For the primary endpoint of slope of eGFR evaluated following initiation of randomized treatment (ie, from Day 1 to Week 108; total slope over 2 years), a mixed-effects model will be fitted to the available eGFR data. The response variable is the eGFR measured at post-baseline assessments for each patient during the double-blind period. The model will include fixed effects for treatment, both stratification factors for randomization, baseline eGFR (continuous), time (in weeks) from baseline (continuous), and time-by-treatment interaction. The model will also include a random intercept and random slope for each patient. The mixed model will utilize restricted maximum likelihood estimation with Kenward-Roger method used to compute the denominator degrees of freedom for tests of fixed effects. The model will assume an unstructured covariance matrix. If the model does not converge under the unstructured covariance matrix, the autoregressive-1 covariance structure will be used. The hypothesis of interest is whether eGFR slopes over the blinded treatment period (after adjusting for early hemodynamic effects) are different between the 2 treatment groups, ie:
 
H0: $\beta_{\text{time}*\text{treatment}} = 0$ versus
 
H1: $\beta_{\text{time}*\text{treatment}} \neq 0$.
 
This hypothesis will be tested using the mixed model by testing whether the time-by-treatment interaction parameter LS mean estimate is equal to zero. Sensitivity analyses are planned to assess the potential impact of major protocol deviations, premature treatment discontinuations, changes in immunosuppressive medications, and the choice of the change point.
 
For the analysis of eGFR absolute change from baseline by visit, a Mixed Model Repeated Measures (MMRM) model will be fitted to the available eGFR data, incorporating all post-baseline visits at which eGFR was measured for each patient during the double-blind period. The model will include treatment, both stratification factors for randomization, baseline eGFR, visit (categorical), and visit-by-treatment interaction as fixed effects. In addition, patient will be included as a random effect. An unstructured within-patient covariance structure will be assumed. If the model does not converge under the unstructured covariance matrix, the autoregressive-1 covariance structure will be used. The LS mean estimate for $\beta_{\text{WKj}*\text{treatment}}$ (ie, the treatment effect at the visit j of interest) from the MMRM model will be used to perform treatment group comparisons by visit.
 
The percent change from baseline to 4 weeks post-cessation of randomized treatment at Week 112 in eGFR will be analyzed via analysis of covariance (ANCOVA). The dependent variable will be the natural log(eGFR) of analysis visit Week 112, with treatment and baseline eGFR in log scale included as fixed effects. The analysis will be stratified by the randomization strata. The treatment effect will be the contrast between sparsentan and irbesartan LS means. The LS means, treatment effect estimate, 95% confidence interval (CI), and p-value will be presented. Estimates and CIs will be converted to percentage.
 
The change from baseline to 4 weeks post-cessation of randomized treatment at Week 112 in eGFR will be analyzed via analysis of covariance (ANCOVA). The dependent variable will be the eGFR at analysis visit Week 112, with treatment and baseline eGFR included as fixed effects. The analysis will be stratified by the randomization strata. The treatment effect will be the contrast between sparsentan and irbesartan LS means. The LS means, treatment effect estimate, 95% confidence interval (CI), and p-value will be presented.
 
For the analysis of eGFR percent change from baseline by visit, a MMRM approach analogous to the model described for the absolute change from baseline will be used, except that the response variable will be natural
	


NAME OF COMPANY: Traverse Therapeutics, Inc.
	
NAME OF FINISHED PRODUCT: sparsentan tablets

log(eGFR) and corresponding baseline value natural log(baseline eGFR). Estimates and CIs will be converted to percentages via the following transformation:
 $[\exp(\text{LS mean change from baseline in natural log(eGFR)}) - 1] \times 100.$ 
For the analysis of eGFR percent change from Week 6 by visit, the estimates from the MMRM model used in the analysis of eGFR relative percent change from baseline by visit described above will be utilized. However, for this analysis, the statistical significance of the treatment difference at visit j (eg, Week 108 for the secondary endpoint) will be assessed by testing the following hypothesis:
 $H_0: (\beta_{\text{WKj}^*\text{treatment}} - \beta_{\text{WK6}^*\text{treatment}}) = 0 \text{ versus } H_1: (\beta_{\text{WKj}^*\text{treatment}} - \beta_{\text{WK6}^*\text{treatment}}) \neq 0,$ 
where $\beta_{\text{WKj}^*\text{treatment}}$ is the treatment effect at the visit j of interest and $\beta_{\text{WK6}^*\text{treatment}}$ is the treatment effect at Week 6. The LS mean estimate from the MMRM model will be used to perform treatment group comparisons by visit. Estimates and CIs will be converted to percentages via the following transformation:
 $[\exp(\text{LS mean change from Week 6 in natural log(eGFR)}) - 1] \times 100.$ 
Analyses of the proportion of patients achieving a UP/C ≤ 1.5 g/g (170 mg/mmol) and a $>40\%$ reduction from baseline at each visit (including the surrogate efficacy endpoint at Week 36) will be performed using a generalized linear model with logit link function to model the probability of achieving UP/C ≤ 1.5 g/g (170 mg/mmol) and a $>40\%$ reduction from baseline and to compare sparsentan with irbesartan. The response variable will be a binary indicator of achievement of UP/C ≤ 1.5 g/g (170 mg/mmol) and a $>40\%$ reduction from baseline at each post-baseline visit. Missing response variables will be imputed using the multiple imputation (MI) procedure before analysis. Fixed effects in the model will include baseline UP/C, treatment, time (categorical, in weeks), and treatment-by-time interaction. Analysis will be stratified by a randomization stratification variable (4 levels based on Screening eGFR and UP/C). An unstructured covariance matrix within patient will be assumed. If convergence issues arise, the autoregressive-1 covariance structure will be used. At each post-baseline visit included in the model, the probability of achieving UP/C ≤ 1.5 g/g (170 mg/mmol) and a $>40\%$ reduction from baseline (risk) for each treatment group, treatment effect (risk difference), standard errors of risk and risk difference, 95% CIs of risks and risk difference, and p-values will be extracted from the model. Relative risk ratios and odds ratios, along with standard errors and 95% CIs, will also be presented. This analysis will be performed at the interim analysis (ie, surrogate efficacy endpoint). Sensitivity analyses will be performed using a Cochran-Mantel-Haenszel (CMH) test at Week 36, tipping point analysis, and analysis using observed cases (ie, no MI).
 
Change from baseline to all post-baseline visits during the double-blind period in natural log(UP/C) will be analyzed using a MMRM model analogous to the one described for percent change from baseline in eGFR. Estimates and CIs will be converted to percentages via the following transformation:
 $[\exp(\text{least-squares mean change from baseline in natural log(UP/C)}) - 1] \times 100$ 
The time to achieve the target reduction in UP/C during the double-blind period will be analyzed using Cox proportional hazards model, stratified by randomization stratification variables, with a comparison between treatment groups. Patients who discontinue from treatment during the double-blind period prior to achieving the target reduction will be censored at the time of treatment discontinuation. Patients who never meet target during the double-blind period will be censored at the time of analysis.
 
The following endpoints will be summarized descriptively for the double-blind period and compared between treatment groups using a CMH test controlling for the randomization stratification variables: the proportion of patients reaching a confirmed 40% reduction in eGFR, ESRD, or death; the proportion of patients requiring initiation or intensification of immunosuppressive medication during the study; and the proportion of patients with reduction in immunosuppressive medication during the study. Changes from baseline to all post-baseline visits during the double-blind period with respect to QoL scores and blood pressure (systolic and diastolic) values will be analyzed using a MMRM model analogous to the one described for changes from baseline in eGFR.
	

NAME OF COMPANY: Traverse Therapeutics, Inc.	NAME OF FINISHED PRODUCT: sparsentan tablets

Safety:
 
All safety analyses for the double-blind period will be conducted based on the Safety Analysis Set.
 
Safety data will include AEs, physical examination results, vital signs, ECG results, and clinical laboratory measurements. Observed data will be listed by patient and summarized using descriptive statistics by treatment group for the double-blind period.
 
Interim Analysis:
 
An unblinded interim analysis will be performed after 36 weeks following randomization of at least 190 patients to evaluate the surrogate endpoint.
 
Open-label Analyses:
 
Analyses of the endpoints for the open-label extension will be performed using the methods described above as appropriate.
 
Efficacy and safety endpoints for the open-label extension will be summarized using descriptive statistics and presented overall and by original randomized treatment based on the OLEFAS. Analyses using baselines other than Week 112 (eg, prior to first dose of study medication in the double-blind period) may be explored.
	

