

NAME OF COMPANY: Travere Therapeutics, Inc.
	
NAME OF FINISHED PRODUCT: sparsentan tablets

STATISTICAL METHODS:
 
Power and Sample Size:
 
Approximately 300 patients will be randomized and allocated 1:1 to receive sparsentan or irbesartan. This sample size takes into consideration enrollment feasibility in this rare disease setting and was evaluated using simulations.
 
For the surrogate endpoint, at the time of the interim analysis (which is planned for after 36 weeks following randomization of at least 190 patients [approximately 95 per treatment group]), the power to detect a difference in response proportions between treatment groups is more than 90%, assuming the response proportions are 50% for sparsentan and 20% for irbesartan, with a 2-sided α of 0.05.
 
For the primary endpoint (slope of eGFR) at the final analysis, the study has at least 90% power to differentiate between treatments if the underlying eGFR slope difference is at least 2.5 mL/min/1.73 m² per year for the chronic slope over 2 years (non-US) or at least 2.1 mL/min/1.73 m² per year for the total slope over 2 years (US). The calculations assume that the separate tests for US and non-US countries are performed at a 2-sided α of 0.05 and that statistically significant difference is demonstrated at the interim analysis of the surrogate endpoint.
 
Analysis Sets:
 
Full Analysis Set (FAS): All patients who are randomized and take at least 1 dose of double-blind study medication will be included in the FAS. All analyses of the FAS will be based on each patient's randomized assigned treatment. If a patient is incorrectly stratified (ie, randomized according to the incorrect stratification), the patient will be analyzed under the randomized treatment for the stratum recorded in the randomization system. All efficacy analyses for the double-blind period will be based on the FAS.
 
Per Protocol (PP) Analysis Set: The PP Analysis Set will include all patients in the FAS who meet the study eligibility requirements and have no major protocol deviations that affect the validity of the efficacy measurements. Patients will be analyzed according to their randomized treatment. The PP Analysis Set will be used for a sensitivity analysis of the primary efficacy endpoint. The criteria for inclusion in the PP Analysis Set will be finalized prior to study unblinding and detailed in the Statistical Analysis Plan.
 
Safety Analysis Set: All patients who are randomized and take at least 1 dose of double-blind study medication will be included in the Safety Analysis Set. Safety analyses will be based on randomized treatment.
 
Open-Label Extension Full Analysis Set (OLEFAS): All patients who received at least 1 dose of open-label sparsentan in the open-label extension will be included in the OLEFAS. All efficacy and safety analyses during the open-label extension will be based on the OLEFAS.
 
Demographics and Baseline Characteristics:
 
Demographic data and baseline characteristics for the FAS, PP, and Safety Analysis Sets will be summarized by treatment group using descriptive statistics. Demographic data include sex, age (years), categorical age (<18 years and ≥18 years), race/ethnicity, weight (kg), height (cm), and calculated BMI. Baseline characteristics also include reproductive status (for females only), HbA1c, baseline eGFR, and current use of: steroids, calcineurin inhibitors, mycophenolate mofetil and other immunosuppressive agents, RAAS inhibitors (ie, angiotensin-converting enzyme inhibitors, ARBs, aldosterone blockers, and aliskiren) prior to the 2-week washout, diuretics, additional antihypertensive treatments, and statins.
 
Likewise, demographic data and baseline characteristics for the OLEFAS will be summarized overall using descriptive statistics.
 
Efficacy:
 
All efficacy analyses during the double-blind period will be performed based on the FAS. The primary endpoint analysis will also be conducted using the PP Analysis Set.
	

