8. TREATMENTS

8.1. Treatments Administered

For the purposes of this protocol, sparsentan is the investigational product, and irbesartan is the active control. When referring to either investigational product (sparsentan) or active control (irbesartan), the term “study medication” is used.

The investigational product doses to be administered in the double-blind period of the study will be dispensed as 200 mg sparsentan tablets over-encapsulated (blinded) with size 00 capsules. The active control doses to be administered in the double-blind period of the study will be dispensed as 75 mg irbesartan tablets over-encapsulated (blinded) with size 00 capsules. The open-label sparsentan doses to be administered in the open-label extension will be dispensed as 200 mg or 400 mg sparsentan tablets.

A dose adjustment will be made for patients whose body weight is ≤ 50 kg at screening; these patients will receive one-half the otherwise specified doses of either sparsentan or irbesartan (weight will be measured at each visit and the dose increased at the Investigator’s discretion if the patient’s weight reaches >50 kg).

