6.3.2. Interim Analysis Set

The IAS is the subset of the FAS at the time of the data extraction for interim analysis (per [Section 5.1](#)). Patients in the IAS will be analyzed according to randomized treatment assignment. All analyses conducted at the time of the interim analysis, including primary analysis of the surrogate endpoint and safety analysis, will be based on the IAS.

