6.3.4. Safety Analysis Set

The Safety Analysis Set includes all patients who are randomized and have taken at least 1 dose of study medication. Patients will be analyzed according to the double-blind randomized treatment. The Safety Analysis Set will be the primary population used for safety analyses.

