7.3. Protocol Deviations

Protocol deviations for missed visits, missed assessments, out of window visits or assessments, and violations of inclusion/exclusion criteria (where possible) will be determined based on available data. All other protocol deviations will be collected through study monitoring.

Protocol deviations that could potentially affect the efficacy or safety conclusions of the study will be identified and the assessment of determination of evaluable patients for analysis populations (PP Analysis Set and PK Analysis) will be performed and approved by the Study Statistician, Medical Monitor, and Clinical Study Manager prior to database lock and unblinding of individual patient treatment information.

Evaluability of patients will be based on the following:

- Compliance of study entry criteria (inclusion and exclusion)
- Correct stratification at randomization
- Received the randomized treatment
- Adequate study medication exposure (no extended dosing interruptions)
- Adequate treatment compliance based on prescribed dose level (within 80% to 120%)
- No prohibited concomitant medications or therapies during the study
- No accidental or intentional unblinding at the investigational site

- No other major protocol deviations that may affect efficacy or safety conclusions, may include:
 - Non-withdrawal although at least 1 withdrawal criterion was met
 - Extensive visit window violations
 - Extensive missing visits
 - Non-adherence to study procedures
 - Inadequate handling of study medication

Major protocol deviations will be summarized by deviation category (overall and due to coronavirus disease 2019 [COVID-19]) and presented in a by-patient data listing.

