10. SAFETY AND TOLERABILITY

Safety analyses will be conducted using the Safety Analysis Set at both interim and final analysis. At the interim analysis, all available data will be summarized. Unless otherwise noted, all safety analyses will be conducted using on-study data. All safety analyses specified below refer to the double-blind period only, except where noted. If >5% of patients initiate RRT while on study, select summaries excluding results after initiation of RRT may be prepared.

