10.1. Adverse Events

Adverse event (AE) data will be collected from the time that signed informed consent is obtained until the patient fully completes his/her participation in the study.

All AE summaries will be restricted to TEAEs, which is defined as any AE that newly appears, increases in frequency, or worsens in severity following the initiation of study medication. If it cannot be determined whether the AE is treatment emergent due to a partial onset date, then it will be counted as treatment emergent. Verbatim terms will be coded to PT and SOCs using MedDRA.

Each AE summary will be displayed by treatment group. Summaries that are displayed by SOC and PT will be ordered by descending order of incidence of SOC and PT within each SOC. Summaries of the following types will be presented:

- Overall summary of TEAEs
- Patient incidence of TEAEs and the total number of entries by SOC and PT
- Patient incidence of TEAEs and the total number of entries by PT in descending order
- Patient incidence of TEAEs by SOC, PT, and highest severity. At each level of patient summarization, a patient is classified according to the highest severity if the patient reported 1 or more events. AEs with missing severity will be considered severe for this summary.
- Patient incidence and total number of entries of severe TEAEs by SOC and PT. AEs with missing severity will be considered severe for this summary.
- Patient incidence of TEAEs by SOC, PT, and closest relationship to study medication (Related/Not Related). Related AEs are those with relationships reported as “Possibly Related” or “Related” and unrelated AEs are those with relationships reported as “Unlikely Related” or “Not Related.” At each level of patient summarization, a patient is classified according to the closest relationship to study medication if the patient reported 1 or more events. AEs with a missing relationship will be considered related for this summary.
- Patient incidence and total number of entries of related TEAEs by MedDRA SOC and PT. AEs with a missing relationship will be considered related for this summary.
- Patient incidence of serious TEAEs and the total number of entries by SOC and PT
- Patient incidence of TEAEs leading to treatment discontinuation by SOC and PT
- Patient incidence and total number entries of treatment-emergent adverse events of interest (AEOIs) by SOC and PT

- Patients incidence and total number of entries of TEAEs associated with safety topics of interest by PT

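### Safety is tabulated by randomized treatment with no as-treated analysis, so a patient given the other study drug for most of treatment would be counted under the wrong drug (minor, free to fix)

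*Protocol*

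**What the plan says.** The grouping rule for safety is the same wherever it appears.

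- Protocol synopsis (Analysis Sets) and Protocol 12.3.3: "Safety analyses will be based on randomized treatment".
- SAP 6.3.4: "Patients will be analyzed according to the double-blind randomized treatment".
- SAP 6.3.2, whose set also covers safety at the interim: "Patients in the IAS will be analyzed according to randomized treatment assignment".

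Membership does not depend on which drug was taken. SAP 6.3.4 says "The Safety Analysis Set includes all patients who are randomized and have taken at least 1 dose of study medication", and Protocol 8.1 defines the last two words to cover both drugs: "When referring to either investigational product (sparsentan) or active control (irbesartan), the term “study medication” is used". A wrongly dosed patient therefore stays in the set, under the randomized arm.

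The tables follow the set. SAP 10: "Safety analyses will be conducted using the Safety Analysis Set at both interim and final analysis". SAP 10.1: "Each AE summary will be displayed by treatment group". Exposure and compliance (Protocol 12.6, SAP 10.2) are also summarized by treatment group.

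The plan does consider receipt of the assigned drug in one place. SAP 7.3 lists "Received the randomized treatment" among the conditions for evaluability, but that list decides entry to the Per Protocol and PK sets only. Neither document defines an actual-treatment variable, plans an as-treated safety table, or says how safety tables handle a patient who was given the other drug.

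**The concern.** For efficacy, analysis by randomized arm protects the comparison. For safety, the question is what happened to people who took sparsentan and to people who took irbesartan. A patient randomized to irbesartan who took sparsentan throughout would contribute any sparsentan reaction, and all weeks of exposure, to the irbesartan column. When the drugs truly differ, such misplacement tends to pull the columns together, which is not the cautious direction for safety.

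With the same members and the same arm assignment as the FAS, the Safety Analysis Set is the FAS under a second name. The plan would let a wrong-drug patient be dropped from the Per Protocol and PK sets while leaving that patient under the randomized drug in every safety table. The outcomes most exposed are those with few events, such as the liver events of interest in SAP 10.1.1 and rare serious adverse events.

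**Working it through.** The documents state no figure on this point, so there is none to reproduce. The rule is a matter of text. The arithmetic below only shows how much it could matter.

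**Inputs**
- n = 150 per arm (about 300 patients allocated 1:1; Protocol 12.2, SAP 4.3.1).
- m = number of patients in each arm who receive the other drug for the whole of treatment. Not given in the documents; assumed range 0 to 10.
- pS and pI = true event risks on sparsentan and irbesartan. Two assumed pairs: 20% vs 10%, and 5% vs 1%.

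**Average effect**

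As-randomized risk in the sparsentan column: [(n − m)pS + m·pI] / n.
As-randomized risk in the irbesartan column: [(n − m)pI + m·pS] / n.
Subtracting gives the displayed difference: (pS − pI)(1 − 2m/n).

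| m per arm | 1 − 2m/150 | true difference 10 points | true difference 4 points |
|---|---|---|---|
| 0 | 1.000 | 10.00 | 4.00 |
| 1 | 0.987 | 9.87 | 3.95 |
| 3 | 0.960 | 9.60 | 3.84 |
| 5 | 0.933 | 9.33 | 3.73 |
| 10 | 0.867 | 8.67 | 3.47 |

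One swapped pair removes 2/150 = 1.3% of the difference; ten pairs remove 20/150 = 13.3%. Grouping by treatment received restores the factor to 1 in every row.

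**Rare events**

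One event placed in the wrong column moves that column's incidence by 1/150 = 0.67 points. Suppose five liver events occur in patients taking sparsentan and none in patients taking irbesartan, and one of the five patients had been randomized to irbesartan. Holding 150 in each column:
- by treatment received: 5/150 − 0/150 = 3.3 points;
- by randomized treatment: 4/150 − 1/150 = 2.0 points.

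This needs the misdosed patient to be one of the few with an event. At 5/150, that chance is about 1 in 30 for any given patient who takes sparsentan.

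**Partial errors**

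A 68-count bottle (Protocol 8.2.1) at 4 capsules a day (Protocol Table 2) lasts 68/4 = 17 days, and 17/(108 × 7) is about 2% of the treatment period. A wrong supply for a full 12-week interval is 12/108 = 11%. In a patient who completes treatment, either error leaves most exposure on the randomized drug, so a rule based on the larger part of exposure would not move that patient. A listing is needed to show those cases.

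**The case against.** The strongest reply is that nothing here is an error. Protocol and SAP state one prespecified rule consistently, it preserves the randomized comparison, and nothing in the documents requires as-treated grouping. Allocation is central through the IWRS, and each bottle carries a medication identification number, so wrong-drug cases should be few. A case might also be noticed: major deviations are summarized and listed by patient (SAP 7.3), both drugs are assayed in plasma at scheduled visits through Week 48, and the DMC may request unblinded individual data (Protocol 13.2). All of this stands, and it is why the point is minor. None of it regroups a safety table.

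Three stronger readings are tempting and are not supported.

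- **That safety results in this trial are distorted.** The SAP 7.3 item is one line in a general evaluability list. It shows that the authors thought of the case, not that it occurred or how often.
- **That a significant safety finding would be lost.** Fisher's exact test gives p = 0.060 for 5/150 vs 0/150 and p = 0.371 for 4/150 vs 1/150, but the plan runs no such test on adverse events. Safety is descriptive, and the liver time-to-event analyses give Kaplan-Meier estimates without a comparison of arms. Fisher's test is planned only for hospitalizations, which are analysed on the FAS as an efficacy endpoint.
- **That events are always credited to a drug never taken.** That is exact only for full-duration errors. For partial errors it applies only to the wrong-drug interval.

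**Conclusion.** The point holds as a contingent weakness in how the safety sets are defined. If a patient receives the other drug for all or most of treatment, the stated rule tabulates that patient's events, laboratory results and exposure under the wrong drug, and no planned analysis corrects it.

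Its size depends entirely on whether such errors happen. With none, nothing changes. The average loss is about 1.3% of a risk difference per swapped pair, assuming full-duration errors in equal numbers in the two arms. The practical risk is confined to rare serious or liver events, where a single patient can change how a table reads. No planned adverse-event test, efficacy result or type I error statement is affected. The open-label extension is not affected in the same way, because every patient there takes sparsentan. Severity is minor; the change is worth making because it is nearly free.

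**What to change.** Make the same edit in the protocol synopsis, Protocol 12.3.3, SAP 6.3.4 and the safety part of SAP 6.3.2. If SAP 6.3.2 is left out, it will contradict 6.3.4 for interim safety. Suggested content:

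- Safety and exposure (SAP 10.2) are analysed by the double-blind treatment actually received. A patient who took both drugs is assigned to the drug taken for the larger part of exposure.
- Every patient who took any wrong-drug doses is listed, with the dates and the adverse events that began during the wrong-drug interval. This makes visible the partial errors that the majority rule does not move.
- The FAS and all efficacy analyses keep randomized assignment.

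The cost is a short edit in four places, one actual-treatment variable derived from the dispensing records (bottles already carry identification numbers), and one listing. The plasma assays of both drugs offer a cross-check through Week 48. At the interim, the variable can be derived by the unblinded statistical subteam, so the blind is not touched.
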